6.5. Post-treatment Assessments

6.5.1. 30-Day Follow-up Assessments

Those subjects who prematurely discontinue study drug and continue in the study through at least one subsequent visit after the Early Study Drug Discontinuation Visit will not be required to complete the 30-Day Follow-Up Visit.

Subjects who prematurely discontinue study drug and refuse to continue in the study through the End of E/C/F/TAF Visit will be asked to return to the clinic 30 days after the completion of the ESDD Visit for the 30-Day Follow-Up Visit.

Subjects who complete the study through the End of E/C/F/TAF Visit and do not continue on the B/F/TAF OL rollover extension will be required to return to the clinic after the End of E/C/F/TAF visit for a 30 Day Follow-Up Visit.

Subjects who prematurely discontinue study drug during the Open-Label rollover extension will be asked to return to the clinic 30 days after the completion of the ESDD Visit for the 30-day Follow-Up Visit. The subject will not continue attending the scheduled study visits.

Subjects who complete the Open-Label rollover extension will be asked to return to the clinic 30 days after the completion of study drug for the 30-day Follow-Up Visit.

For the purpose of scheduling a 30-Day Follow-Up Visit, a \pm 6 days window may be used. The following evaluations are to be completed at the 30-Day Follow-Up Visit:

- Review of AEs and changes in concomitant medications
- Symptom-directed physical examination as needed
- Weight
- Blood sample collection for the following laboratory analyses:
 - Chemistry profile: alkaline phosphatase, AST, ALT, total bilirubin, direct and indirect bilirubin, total protein, albumin, CPK, bicarbonate, BUN, calcium, chloride, creatinine, glucose, phosphorus, magnesium, potassium, sodium, uric acid, amylase (reflex lipase testing is performed in subjects with total amylase $> 1.5 \times$ ULN) and PTH.
 - Sample should be drawn prior to hemodialysis
 - Timing of draw and timing of hemodialysis should be recorded
 - Hematology profile: CBC with differential and platelet count
 - Plasma HIV-1 RNA (Taqman v2.0)
 - CD4+ T cell count
 - Serum pregnancy test (females of childbearing potential only)
 - Serum and plasma storage samples for possible additional clinical testing (for subjects who provide consent)

At the 30 Day Follow Up Visit, any evaluations showing abnormal results believed to be a reasonable possibility of a causal relationship with the study drug will be repeated weekly (or as often as deemed prudent by the Investigator) until the abnormality is resolved, returns to baseline, or is otherwise explained.

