7.3.1. Adverse Events

Following initiation of study drug, collect all AEs, regardless of cause or relationship, until 4 weeks after last administration of study drug must be reported to the eCRF database as instructed.

All AEs should be followed up until resolution or until the adverse event is stable, if possible. Gilead Sciences may request that certain AEs be followed beyond the protocol defined follow up period.

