8.5.2. Adverse Events

Clinical and laboratory adverse events will be coded using the Medical Dictionary for Regulatory Activities (MedDRA). System Organ Class (SOC), High-Level Group Term (HLGT), High-Level Term (HLT), Preferred Term (PT), and Lower-Level Term (LLT) will be attached to the clinical database.

Treatment-emergent adverse events are adverse events that meet one of the following criteria:

- Adverse events with onset dates on or after the first dose date of study drug, and no later than 30 days after permanent discontinuation of study drug, or
- Adverse events that result in permanent study drug discontinuation

Summaries (number and percentage of subjects) of treatment-emergent adverse events (by SOC, HLT [if applicable], and PT) will be provided. Additional summaries will include summaries for adverse events by grade, Investigator's assessment of relationship to study drug, and effect on study drug dosing.

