8.5.3. Laboratory Evaluations

Selected laboratory data will be summarized using only observed data. Absolute values and changes from baseline at all scheduled time points will be summarized.

Graded laboratory abnormalities will be defined using the GSI Grading Scale for severity of Adverse Events and Laboratory Abnormalities ([Appendix 6](#)).

Incidence of treatment-emergent laboratory abnormalities, defined as values that increase at least one toxicity grade from baseline at any time post baseline up to the date of last dose of study drug plus 30 days, will be summarized. If baseline data are missing, then any graded abnormality (i.e., at least a Grade 1) will be considered treatment-emergent. The maximum toxicity grade will be summarized by laboratory parameter.

Laboratory abnormalities that occur before the first dose of study drug or after the subject has been discontinued from treatment plus 30 days will be included in a data listing.

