c All study visits are to be scheduled relative to the Day 1 Visit date. Visit windows are \pm 2 days of the protocol specified date through Week 12, \pm 6 days of the protocol specified date through Week 48, except Week 48. Weeks 48 Visit window is \pm 6 weeks of the protocol specified date. Week 48 Visit should be completed within \pm 6 day window, unless otherwise specified by the Sponsor. Following the Week 48 Visit, study visits are to be completed within \pm 6 days of the protocol specified date through Week 84. The visit window at Week 96 will be \pm 6 weeks of the protocol-specific visit date. Unless notified by the Sponsor, Week 96 Visit should be completed within \pm 6 days of the protocol-specific visit date.

d Required for those subjects who complete Week 96 Visit or those subjects who prematurely discontinue study drug and do not continue in the study through at least one subsequent visit after the Early Study Drug Discontinuation Visit. For the purpose of scheduling a 30-Day Follow-Up Visit, a \pm 6 days window may be used.

e Early Study Drug Discontinuation Visit to occur within 72 hours of last dose of study drug. Subjects will be asked to continue attending the scheduled study visits through Week 96, if the subject discontinues study drug prior to completion of Week 96 Visit.

f Complete physical examination (urogenital/anorectal exams will be performed at the discretion of the Investigator).

g Symptom-directed physical examination as needed

h Weight only

i Chemistry profile: alkaline phosphatase, AST, ALT, GGT, total bilirubin, direct and indirect bilirubin, total protein, albumin, LDH, CPK, bicarbonate, BUN, calcium, chloride, creatinine, glucose, phosphorus, magnesium, potassium, sodium, uric acid, PT/INR, amylase (reflex lipase testing is performed in subjects with total amylase $> 1.5 \times$ ULN) and PTH. At Day 1, Weeks 24, 48, 72, and 96 analyses of glucose will be done as part of the fasting metabolic assessments and not as part of the chemistry profile. PT/INR will be included in the chemistry profile at Screening, Weeks 24 and 48 only. This sample should be drawn prior to hemodialysis. The timing of draw and timing of hemodialysis should be recorded.

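### In the E/C/F/TAF phase, the rules for collecting safety data after an early drug stop do not match the 30-day treatment-emergent window

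*Protocol*

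**What the plan says.** **Analysis window.** Protocol 8.5.2 counts an AE as treatment-emergent if it starts on or after the first dose and "no later than 30 days after permanent discontinuation of study drug". SAP 8.3.5.1 uses the same limit for subjects who do not enter the B/F/TAF extension. Protocol 8.5.3 counts laboratory abnormalities "at any time post baseline up to the date of last dose of study drug plus 30 days", and SAP 8.4.2.1 agrees.

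**AE collection.** Protocol 7.3.1 requires all AEs "until 4 weeks after last administration of study drug must be reported to the eCRF database as instructed". Section 7.3.2 goes further for serious AEs: they are reported throughout the study, and serious AEs and deaths within 30 days of the last dose are reported in any case.

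**The 30-Day Follow-Up Visit.** The first paragraph of Protocol 6.5.1 says early stoppers who "continue in the study through at least one subsequent visit after the Early Study Drug Discontinuation Visit will not be required to complete" this visit. Footnote d of Appendix 2, repeated in SAP Appendix 1, requires it of early stoppers only if they "do not continue in the study through at least one subsequent visit after the Early Study Drug Discontinuation Visit". Neither states an interval from the last dose. The second paragraph of 6.5.1 reads differently: "Subjects who prematurely discontinue study drug and refuse to continue in the study through the End of E/C/F/TAF Visit will be asked to return" for the visit.

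**Timing.** Those early stoppers "will be asked to return to the clinic 30 days after the completion of the ESDD Visit", within 6 days either side. The ESDD Visit itself falls up to 72 hours after stopping (6.5.2).

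**Extension.** There is no waiver there: "Subjects who prematurely discontinue study drug during the Open-Label rollover extension will be asked to return to the clinic 30 days after" the ESDD Visit.

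**The concern.** The primary objective is safety, and the primary endpoint is the incidence of treatment-emergent Grade 3 or higher AEs to Week 48, with the same measure to Week 96 as a secondary endpoint. Both depend on the 30-day tail being observed for subjects who stop drug early. Non-serious Grade 3 events in the last two days of the tail count in the analysis but need not be collected. A subject excused the follow-up visit may have no laboratory draw late in the tail. One who attends may have the draw too late to count. Each gap can only lower the reported counts. The conflict between the two paragraphs of 6.5.1 also lets sites treat the same subject differently, and a site working from the footnote would apply the waiver.

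**Working it through.** **The plan's own figure.** Protocol 8.7 gives a 95% interval for n = 50 and a 10% rate: 0.10 ± 1.96 × √(0.10 × 0.90 / 50) = 0.10 ± 0.083, or 1.7% to 18.3%. It reproduces, and nothing below changes it.

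**1. AE collection against AE window.** 4 weeks = 28 days. 30 − 28 = 2 days, or 2/30 = 6.7% of the window, in which non-serious AEs count but need not be collected.

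**2. Day of the follow-up visit for early stoppers.** Day after last dose = L + 30 ± 6, where L is the ESDD lag (0 to 3 days).

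| L | Permitted days | Of 13 days, number after day 30 |
|---|---|---|
| 0 | 24 to 36 | 6 |
| 1 | 25 to 37 | 7 |
| 2 | 26 to 38 | 8 |
| 3 | 27 to 39 | 9 |

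**3. The waiver, by example.** Last dose Day 158, ESDD Day 160, Week 24 visit Day 168. The waiver condition is met 168 − 158 = 10 days after the last dose. If the subject stays, the next scheduled draw is Week 36, Day 252, which is 94 days after the last dose. If the subject leaves, the first paragraph of 6.5.1 excuses the 30-day visit and the second asks for it.

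**4. How often the schedule allows this.** Assume drug stops are spread evenly over Days 1 to 670, with visits on nominal Days 14, 28, 56, 84 and then every 84 days to 672. Count the days on which the next scheduled visit after ESDD comes less than 30 days after the last dose:

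- L = 0: 285/670 = 42.5%. L = 3: 258/670 = 38.5%.
- Stops before Day 84: 83/83 = 100% at L = 0, and 76/83 = 92% at L = 3.
- Stops from Day 84: 202/587 = 34.4% at L = 0, and 182/587 = 31.0% at L = 3.

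On the other 57.5% to 61.5% of stopping days the next visit falls on day 30 or later. Day 30 itself apart, no scheduled draw after ESDD is then inside the window. A stop on Day 170, for instance, has its next visit on Day 252, 82 days later.

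**5. Effect on the Grade 3 or higher rate.** Protocol 1.2.5 reports 18 of 55 subjects with a Grade 3 or 4 event to Week 48. Constant hazard = −ln(1 − 18/55) / 336 = 0.00118 per day. Assume 7 early stoppers, borrowing the 7 subjects in the same section who stopped early and lacked Week 48 virologic data.

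- 2 days unobserved: 1 − exp(−2 × 0.00118) = 0.24% each. 7 × 0.0024 = 0.016 subjects, and 0.016/55 = 0.03 percentage points.
- 27 of the 30 days unobserved in all 7 (ESDD on day 3, then nothing): 1 − exp(−27 × 0.00118) = 3.1% each. 7 × 0.0314 = 0.22 subjects, and 0.22/55 = 0.40 points.

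**The case against.** The strongest reply is that little is actually lost.

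- Early stoppers are asked to keep attending to Week 96, with AE review at every visit on or off drug (Protocol 6.3, 6.5.2). AEs are classified by onset date, so a later visit can still record an event from days 11 to 28.
- Related laboratory abnormalities at ESDD are repeated weekly until resolved or explained (6.5.2). Clinically significant Grade 3 and 4 results are repeated within 3 days (7.6).
- An AE that leads to discontinuation is treatment-emergent whatever its date (8.5.2).
- Laboratory values after day 30 are still listed (8.5.3).
- Only 3 of 55 subjects had stopped for an AE at the interim (1.2.5).

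All of this stands, and it keeps the numerical effect small. It does not remove the two-day AE gap or the conflict within 6.5.1. Nor does it recover routine laboratory values never drawn inside the window.

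A reader might infer more than the documents support. AE collection as a whole does not end at 4 weeks, because serious AEs and deaths run to day 30. A subject who attends one visit and then leaves is not plainly lost, because the second paragraph of 6.5.1 asks that subject back. The shares in step 4 show how often the waiver condition can be met before day 30. They do not measure how often data are lost: those subjects do have a scheduled draw inside the window, though possibly an early one.

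**Conclusion.** The mismatch is real and confined in size. In the E/C/F/TAF phase the 30-day window is not fully matched by the 28-day collection of non-serious AEs, by a waiver with no minimum interval that conflicts with the paragraph after it, or by a follow-up visit that can fall on day 24 to 39.

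The expected effect on the Grade 3 or higher AE rate is about 0.03 to 0.40 points of under-count, against a planned interval half-width of 8.3 points. That range rests on a constant hazard from the interim data and an assumed 7 early stoppers. Subjects who stop for toxicity may have a higher hazard, for which the documents give no figure. Against that, the hazard includes serious events, which are collected anyway. A reader might infer that the primary endpoint is materially biased; the figures do not support that. The case for change is that the window the analysis relies on should be observable and the instructions consistent, at little cost.

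**What to change.** - **Protocol 7.3.1:** collect all AEs for at least 30 days after the last dose instead of 4 weeks.
- **Protocol 6.5.1 and footnote d (Protocol Appendix 2, SAP Appendix 1):** reconcile the two paragraphs and the footnote. Waive the 30-Day Follow-Up only when a scheduled visit with AE review and a laboratory draw falls within the permitted window around 30 days after the last dose. Waiving it whenever the next visit is at least 30 days out would secure AE recall, but would keep the laboratory gap for the 57.5% to 61.5% of stopping days in step 4.
- **Timing:** count the visit from the last dose, not from ESDD, which gives day 24 to 36.
- **SAP 8.4.2.1 and 8.4.2.2, with Protocol 8.5 and 8.5.3 aligned:** state that laboratory results from a 30-Day Follow-Up Visit held within its permitted window are included. Without the protocol alignment this would create a new mismatch.

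**Cost:** wording changes, one existing visit for the few early stoppers now excused, and a few off-drug laboratory values up to day 36 in the treatment-emergent tables.

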6.5.2. Early Study Drug Discontinuation Assessments (ESDD)

Subjects who have discontinued study drug prior to the Week 96 or End of E/C/F/TAF Visit will not be eligible for the open-label rollover extension study; these subjects will be asked to return to the clinic within 72 hours of stopping the study drug for the Early Study Drug Discontinuation Visit. The subject will be asked to continue attending the scheduled study visits through Week 96 Visit (if applicable).

Every attempt should be made to keep the subject in the study through Week 96 Visit and continue to perform the required study-related follow-up and procedures (see Section 6.5.3, Criteria for Discontinuation of Study Treatment). If this is not possible or acceptable to the subject or investigator, the subject may be withdrawn from the study.

If the subject discontinues study drug during the Open-Label rollover extension, the subject will be asked to return to the clinic within 72 hours of stopping the study drug for the Early Study Drug Discontinuation Visit.

At the Early Study Drug Discontinuation Visit, any evaluations showing abnormal results indicating that there is a possible or probable causal relationship with the study drug, should be repeated weekly (or as often as deemed prudent by the Investigator) until the abnormality is resolved, returns to baseline, or is otherwise explained.

The following evaluations are to be completed at the Early Study Drug Discontinuation Visit

- Review of AEs and changes in concomitant medications
- Complete physical examination (urogenital/anorectal exams will be performed at the discretion of the Investigator)
- 12-lead ECG performed supine
- Vital signs (blood pressure, pulse, respiration rate, and temperature) and weight
- Blood sample collection for the following laboratory analyses:
 - Chemistry profile: alkaline phosphatase, AST, ALT, GGT, total bilirubin, direct and indirect bilirubin, total protein, albumin, LDH, CPK, bicarbonate, BUN, calcium, chloride, creatinine, glucose, phosphorus, magnesium, potassium, sodium, uric acid, amylase (reflex lipase testing is performed in subjects with total amylase $> 1.5 \times$ ULN) and PTH
 - Sample should be drawn prior to hemodialysis
 - Timing of draw and timing of hemodialysis should be recorded
 - Estimated GFR according to the Cockcroft-Gault formula for creatinine clearance
 - Hematology profile: complete blood count (CBC) with differential and platelet count
 - Plasma HIV-1 RNA (Taqman v2.0)
 - Subjects who meet the criteria for virologic rebound should be managed according to Management of Suspected Virologic Failure (Section 6.7.1).
 - CD4+ T cell count

- Plasma sample for virology testing or pharmacokinetic testing
- Serum and plasma storage samples for possible additional clinical testing (for subjects who provide consent)
- Serum pregnancy test (females of childbearing potential only)
- SF-36, HIV-TSQc and VAS questionnaires should be completed by the subject. Subject is to read the questionnaire by him/herself and write/mark answers directly onto the questionnaire.
- Site-administered questions for Health Utilization Assessment to be completed
- Drug accountability

6.5.3. Criteria for Discontinuation of Study Treatment

Study drug may be discontinued in the following instances:

- Intercurrent illness that would, in the judgment of the investigator, affect assessments of clinical status to a significant degree. Following resolution of intercurrent illness, the subject may resume study dosing at the discretion of the investigator.
- Unacceptable toxicity, or toxicity that, in the judgment of the investigator, compromises the ability to continue study-specific procedures or is considered to not be in the subject's best interest
- Lack of efficacy
- Subject request to discontinue for any reason
- Subject noncompliance
- Pregnancy during the study; refer to [Appendix 7](#)
- Discontinuation of the study at the request of Gilead, a regulatory agency or an institutional review board or independent ethics committee (IRB/IEC)

[figure not shown]
6.6. Other Evaluations

6.6.1. CCI

CCI

CCI

6.6.2. Blood Storage

From subjects who provide additional consent, a portion of the blood drawn at all visits (except the Screening Visit and Unscheduled Visits) will be frozen and stored. These stored blood samples may be used by the Sponsor or its research partners for future testing to learn more about how the study drug has worked against HIV-1 or clinical laboratory testing to provide additional safety data. No human genetic testing will be performed without expressed consent of study subjects. At the conclusion of this study, these samples may be retained in storage by Gilead Sciences, Inc. for a period up to 15 years.

6.7. Virologic Failure

Subjects who experience virologic rebound (VR), as defined below, will be considered to have virologic failure.

Subjects will be considered to have virologic rebound if they have confirmed HIV-1 RNA ≥ 50 copies/mL (two consecutive tests) at a scheduled or unscheduled visit.

6.7.1. Management of Virologic Failure

- If the viral load is ≥ 50 copies/mL, HIV-1 RNA should be repeated at a scheduled or unscheduled visit (2-4 weeks after the date of the original test with HIV-1 RNA ≥ 50 copies/mL).
- Upon confirmation of HIV-1 RNA ≥ 50 copies/mL, potential causes of virologic failure should be documented. Assessments should include:
 - Adherence
 - Concomitant medication
 - Comorbidities (for example: active substance abuse, depression, other intercurrent illnesses)
- If virologic rebound is confirmed, and the HIV-1 RNA is < 400 copies/mL, subjects may remain on their current regimen at the discretion of the Investigator. Subject will return for a repeat within 2-4 weeks.

[figure not shown]
- If virologic failure is confirmed at the scheduled or unscheduled visit and HIV-1 RNA value is ≥ 400 copies/mL, the blood samples from the confirmation visit will be used for HIV-1 genotype/phenotype testing.
- If genotype/phenotype resistance to study drug is documented, study drugs should be discontinued.
- If no resistance is detected from genotype/phenotype testing, subject may remain on study drug and HIV-1 RNA should be repeated (2-4 weeks from the date of confirmed test with HIV-1 RNA ≥ 50 copies/mL). Investigators should carefully evaluate the benefits and risks of remaining on study drug for each individual subject and document this assessment in the subject's source documents. Investigators who opt to discontinue study drugs for an individual subject must discuss with the Medical Monitor prior to study drug discontinuation.

6.7.2. Subjects with ≥ 400 copies/mL of HIV-1 in the Absence of VR

Subjects with HIV-1 RNA < 50 copies/mL could subsequently experience unconfirmed blips of HIV-1 RNA ≥ 400 copies/mL. Such subjects will be analyzed for resistance if the unconfirmed rebound happens at Week 24, Week 48, Week 96, any visit prior to the End of E/C/F/TAF Visit or at the last visit while receiving study drugs (or within 72 hours of discontinuation of study treatment).

Please refer to [Figure 6-1](#) for the management of subjects who meet the criteria for virologic failure.

Figure 6-1. Schema for Management of Virologic Failure (E/C/F/TAF)

a If virologic rebound is not confirmed, the subject will remain on their current regimen.

b If virologic rebound is confirmed, and the HIV-1 RNA is < 400 copies/mL, subjects may remain on their current regimen at the discretion of the Investigator. Subject will return for a repeat within 2-4 weeks. If virologic rebound is confirmed, and HIV-1 RNA is ≥ 400 copies/mL, the HIV-1 genotype and phenotype (reverse transcriptase, protease, and, if applicable, integrase resistance) will be analyzed.

c Based on the results of the genotype/phenotype assays, the subject will remain on study drugs or study drugs will be discontinued. If genotyping/phenotyping assay fails, a new ARV regimen may be configured at the discretion of the Investigator.

d If no resistance detected, HIV-1 RNA will be repeated (2-4 weeks later). Investigator reviews study drug continuation/discontinuation options and discuss with Medical Monitor prior to study drug discontinuation.

e A new ARV regimen will be configured, at the Investigator's discretion, and the subject will remain in the study.

